While the primary comparison of interest for efficacy endpoints will be within Cohort 2, for IMG-007 [REDACTED] versus placebo group, a broader comparison including 300 mg group versus placebo and the combined 300 mg and [REDACTED] versus placebo are also of additional, exploratory interest. For analysis within Cohort 1 (i.e., 300 mg group), efficacy comparison with baseline at each visit will be performed based on difference relative to zero. All analysis will use nominal two-sided significance level of 0.05.

For continuous efficacy endpoints, a mixed-effect model with repeated measures (MMRM) will be used. This model includes visit as a factor and respective baseline score as covariate for both Cohorts 1 & 2, and additionally treatment and treatment-by-visit interaction as factors for Cohort 2 only. Specific ways of handling data after receiving rescue medication or any other such clinical events will be performed.

For binary efficacy endpoints, if high potency corticosteroids or systemic rescue medications are used, the participant will be reported as a non-responder from the time such rescue medication is used.

Sensitivity analysis using other missing data handling approaches will also be performed. Further details including handling of specific intercurrent events and missing data imputations will be specified in the prospective statistical analysis plan (SAP).

PK Analyses

Serum concentration data will be tabulated and summarized (geometric mean, arithmetic mean, minimum, maximum, SD and % coefficient of variation) by treatment group for each visit at which samples were taken.

Immunogenicity Analyses

The immunogenicity results will be summarized using descriptive statistics by the number and percentage of participants who develop detectable ADA. The incidence of positive ADA will be reported for evaluable participants.

PD Analyses

Biomarker data will be listed by participant and visit/timepoint. Data for skin punch biopsy will be listed and summarized by visit.

Timing of Analyses

Timing of Analyses

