7.2 Data Handling Convention Missing Data

Missing data will not be imputed in listings. This section includes the methods for missing data imputation for some summary analyses, if necessary.

Adverse event

If the intensity of a TEAE is missing, it will be classified as “severe” in the frequency tables by intensity of TEAE. If the assessment of relationship of a TEAE to the investigational product is missing, it will be classified as “related” in the frequency tables by relation to the investigational product.

The partial date values will be imputed as specified in the [Appendix 12.2](#). Imputed dates will not be presented in the listings.

[figure not shown]

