12.2 Partial Date Conventions

Algorithms for Adverse Events, Medical History, and Prior and Concomitant Medications

Partial date to be imputed as:

Start Date	Stop Date	Action
Complete	Complete	No action
Partial, but known components shows it can't be on or after study medication start	Complete	Impute the start date as "01", if only the day is missing. Impute the start date as "01 January", if month and day are missing.
	Date and/or month missing	Impute the stop date as the latest possible date (i.e., last day of the month, if only the day is missing or "31 December" if month and day are missing).
Partial, could be on or after the study medication start Or missing	Complete	
1) If stop date < study medication start then, Impute the start date as earliest possible date (i.e., "01", if only the day is missing or "01 January", if month and day are missing).2) If stop date \geq study medication start then, impute the start date equal to the study medication start date.
	Partial	Impute the stop date as the latest possible date (i.e., last day of the month, if only the day is missing or "31 December" if month and day are missing). then, 
1) If stop date < study medication start then, impute earliest possible date.2) If stop date \geq study medication start, then impute the start date equal to the study medication start date.
	Missing	Missing date will not be imputed.

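### SAP 12.2 imputes partial stop dates with no cap at the participant's last study date, and gives no start date to a record with a partial or missing start and a missing stop

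*SAP*

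**What the plan says.** SAP 7.2 says of adverse event dates: "The partial date values will be imputed as specified in the" Appendix 12.2. The single table there is headed "Algorithms for Adverse Events, Medical History, and Prior and Concomitant Medications", so it governs rescue medication as well as AEs.

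- **Partial stop.** The instruction is "Impute the stop date as the latest possible date", explained as the last day of the month, or 31 December when day and month are both missing. No upper limit appears in 12.2 or in the readable text of SAP 6.3, 6.9.1 or 7.2.
- **Start that could be post-dose.** The relevant block is "Partial, could be on or after the study medication start Or missing". If the stop is complete or partial and falls on or after first dose, the rule is to "impute the start date equal to the study medication start date". If the stop precedes first dose, the earliest possible date is used. If the stop is missing, the row says only "Missing date will not be imputed".

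These dates feed the rescue duration in SAP 6.3 (last use minus first use plus 1, summed over occasions) and the SAP 6.9.1 table of TEAEs occurring in the treatment period. SAP 4.3 records medications only up to the EOS visit, and SAP 4.6.1 collects AEs only to the end of the study. SAP 7.2 adds: "Imputed dates will not be presented in the listings".

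**The concern.** The stop rule can create dates outside the period in which the SAP itself collects data. A rescue course that must have ended, as far as it was recorded, by the last visit can be assigned a stop weeks or months later. The duration summary then reports time that nobody observed.

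The start rule has a gap. A missing stop is the normal state of an event or medication still ongoing at the last visit: protocol 8.2.2 has AEs unresolved at that visit followed without further eCRF entry. If the start of such a record is also incomplete, no rule places it in time. A record with the same partial start and a known stop is placed.

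At stake are a descriptive rescue-duration summary and the treatment-period TEAE table, in a cohort of 13. Imputed dates are kept out of the listings, so a reader could not see there what had been done.

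**Working it through.** **Inputs.** Cohort 1 enrolled 13 participants between 18 July 2023 and 31 January 2024 (protocol 4.1). The EOS visit is Day 169 (protocol 7.1.5). Assumptions: first dose on the enrolment date, and the last visit exactly on Day 169. The ±3-day visit window would shift each overrun by at most 3 days.

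**1. The plan's own figure.** Week 24 is Day 24 × 7 + 1 = 169, which agrees with the protocol.

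**2. End-of-study dates** (first dose + 168 days).
- First enrolled: 18 July 2023 + 168 = 2 January 2024.
- Last enrolled: 31 January 2024 + 168 = 17 July 2024.

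Every completer therefore ends in 2024.

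**3. Only the day of the stop is missing, in the EOS month.**
- First enrolled: the stop becomes 31 January 2024, which is 29 days after EOS.
- Last enrolled: the stop becomes 31 July 2024, which is 14 days after EOS.
- Over all possible first-dose dates the overrun is 0 to 30 days. The maximum arises when EOS falls on the first of a 31-day month.

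**4. Only the year of the stop is known (2024).** The stop becomes 31 December 2024.
- First enrolled: 364 days after 2 January 2024.
- Last enrolled: 167 days after 17 July 2024.

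**5. Rescue duration when the start is also partial.** The table then sets the start to first dose, and EOS falls on Day 169, so duration = 169 + overrun.

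| Stop known as | First enrolled | Last enrolled |
|---|---|---|
| Month and year (EOS month) | 169 + 29 = 198 days | 169 + 14 = 183 days |
| Year only (2024) | 169 + 364 = 533 days | 169 + 167 = 336 days |

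With a cap at EOS, each of these is at most 169 days. The table has no row for a complete start with a partial stop. If a programmer extends the same convention to that case, the stop overruns in steps 3 and 4 apply unchanged.

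**6. Partial or missing start, missing stop.** No start date results. Study day is undefined, and so is last use minus first use plus 1. If the phrase in that row refers only to the stop, the row still gives no rule for the start.

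**7. Neighbouring rows.** Take first dose 18 July 2023, a start known as November 2023 and a stop of 20 November 2023. The table pulls the start back to 18 July, giving 126 days. The record allows at most 20 days (1 to 20 November). A repair confined to missing stops would give an ongoing record a start of 1 November and a resolved one a start of 18 July.

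**The case against.** The strongest reply is that few records are exposed and the large figures are contrived. For the first participant, EOS is 2 January 2024, so a stop recorded as 2024 could only be 1 or 2 January, and the site would have to lose both day and month. Rescue is prescribed by the investigator, visits are one to four weeks apart, and data discrepancies are queried. This stands: the year-only case is an extreme, and the missing-day case is the realistic one. Nothing in the documents shows how many records have partial dates.

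It can also be said that the phrase about missing dates merely leaves a missing stop open, so that the record stays ongoing. That is a fair reading of the stop, but it leaves the start without a rule.

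The primary endpoint is not at risk. SAP 4.6.1 treats every AE collected in the treatment and follow-up period as a TEAE, whatever its imputed start. Protocol 11.3.1 asks for TEAE duration, but SAP 6.9.1 lists no such table.

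A reader might infer that undated rescue inflates responder rates, because the protocol synopsis counts a participant as a non-responder "from the time such rescue medication is used". The documents do not support that step. No readable text says that undated rescue is treated as no rescue. SAP 4.3 still classes a medication ongoing during the study as concomitant whatever its start date. The operative intercurrent-event text (SAP 6.8.2.2 and 12.7, protocol 11.3.3) is redacted and may contain its own rule.

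**Conclusion.** Two defects in the SAP 12.2 table hold.

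- The stop rule has no cap. Imputed stops can pass end of study by up to 30 days when only the day is missing, and by 167 to 364 days for a completer whose stop is known only as 2024. Rescue duration can then exceed 169 days.
- A record that lacks both a complete start (one that could be on or after first dose) and any stop date receives no start date. Its rescue duration and its place in the treatment-period TEAE table are undefined.

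The figures assume first dose on the enrolment date and EOS on Day 169. The number of affected records is unknown, but among 13 participants one such record could visibly shift a duration summary.

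It would go too far to say that ongoing events in general lose their start day: a record with a complete start keeps it. Overall TEAE incidence is unaffected, and an effect on responder status can be neither asserted nor excluded. This is a correction to descriptive outputs, worth making before programming is final.

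**What to change.** Amend SAP 12.2 as follows.

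1. Impute any partial stop as the earlier of the latest date its known parts allow and the participant's last study date. State that this also applies when the start is complete, which the table does not now cover.
2. For every partial start that could be on or after first dose, unless the stop is before first dose, impute the later of the first-dose date and the earliest date the known parts allow. Apply this whether the stop is complete, partial or missing. A wholly missing start has no known parts and so takes the first-dose date, as the table already does when a post-dose stop exists.
3. Leave a missing stop as ongoing.

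Item 2 must replace the start rule in every row of that block, or resolved and ongoing records with the same partial start will get different dates. In the November example both would then start on 1 November 2023, and the resolved one would last 20 days.

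The cost is a rewrite of one block of an appendix table and the matching derivation code. No new data are needed.

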12.3 Eczema Area and Severity Index (EASI)

The EASI scoring system uses a defined process to grade the severity of the signs of eczema and the extent affected:

1. Select a body region

Four body regions are considered separately:

- Head and neck
- Trunk (including the genital area)
- Upper extremities
- Lower Extremities (including the buttocks)

2. Assess the extent of eczema in that body region

Each body region has potentially 100% involvement. Using the table below, give each respective body region a score between 0 and 6 based on the percentage involvement. Precise measurements are not required.

% involvement	0	1-9%	10 - 29%	30 - 49%	50 - 69%	70 - 89%	90 - 100%
Region score	0	1	2	3	4	5	6

3. Assess the severity of each of the four signs in that body region:

1. Erythema
2. Edema/papulation
3. Excoriation
4. Lichenification

Grade the severity of each sign on a scale of 0 to 3:

- Take an average of the severity across the involved region.
- Half points (1.5 and 2.5) may be used. 0.5 is not permitted – if a sign is present, it should be at least mild (1)
- Palpation may be useful in assessing edema/papulation as

How to record your scores

The assessed parameters are inserted into a table (example shown below for age \geq 8 years). The final EASI score ranges from 0-72.

Body region	Erythema	Edema/ papulation	Excoriation	Lichenification	Area score	Multiplier	Score
Head/neck	(+	+	+)	X	X 0.1	
Trunk	(+	+	+)	X	X 0.3	
Upper extremities	(+	+	+)	X	X 0.2	
Lower extremities	(+	+	+)	X	X 0.4	
The final EASI score is the sum of the 4 region scores							<hr/> (0-72)

12.4 SCORing Atopic Dermatitis (SCORAD) Index

Please refer to Dermatology 1993;186:23-31. doi: 10.1159/000247298. for the assessment of SCORAD index.

Grading of Intensity Items (Objective Signs):

Six items have been selected: (1) erythema. (2) edema/papulation. (3) oozing/crusts. (4) excoriations, (5) lichenification. (6) dryness.

Each item should be graded 0-3 (0=absent; 1 = mild; 2= moderate; 3 = severe) according to reference photographs (see 'Atlas', i.e. fig. 1-15 in Dermatology 1993;186:23-31. doi: 10.1159/000247298). Half-point scoring is not recommended. The area chosen for grading must be representative (average intensity) for each item in a given participant as determined by the investigator, thus excluding one 'target' area or the worst affected site. The same site may however be chosen for 2 or more items. For example, one site may serve for evaluation of both excoriations and erythema. On the other hand, dryness must be appreciated on areas not involved by acute lesions or lichenifications.

Grading Extent:

The rule of nine is detailed in the front-back drawing on the evaluation sheet with a variant (head and lower limbs) for participants under 2 years of age. Lesions taken into account must include only inflammatory lesions and not dryness. In practice it is recommended to draw directly the extent of individual lesions on the printed figure of the evaluation sheet. Note that one participant's palm represents 1% of his body surface.

Subjective Items:

These include pruritus and sleep loss. Make sure that the participant (generally over 7 years) or his/her parents is/are capable of answering properly. Ask him/her to indicate on the 10-cm scale of the assessment form the point corresponding to the average value for the last 3 days/nights.

Copyright Pr. JF Stalder-ETFAD-2014

SCORAD
EUROPEAN TASK FORCE ON ATOPIC DERMATITIS

INSTITUTION _____

PHYSICIAN _____

First name _____

Last name _____

Date of Birth _____ DD/MM/YY

Date of Visit _____

Figures in parenthesis for children under two years

A: EXTENT Please indicate the area involved _____

B: INTENSITY _____

CRITERIA	INTENSITY
Erythema	_____
Edema/Papulation	_____
Oozing/crust	_____
Excoriation	_____
Lichenification	_____
*Dryness	_____

Intensity items (average representative area)
0=absent
1=mild
2=moderate
3=severe

*Dryness is evaluated on unininvolved area

C: SUBJECTIVE SYMPTOMS
PRURITUS + SLEEP LOSS _____

SCORAD= A/5+7B/2+C _____

PRURITUS (0 to 10) _____ 0  10

SLEEP LOSS (0 to 10) _____ 0  10

Visual analog scale (average for the last 3 days or nights)

12.5 Handling of items from DLQI

- I. If one question is left unanswered this is scored 0 and the scores are summed up and expressed as usual out of a maximum of 30.
- II. If two or more questions are left unanswered the questionnaire is not scored.
- III. If question 7 is answered 'yes' this is scored 3 even if in the same question one of the other boxes is ticked.
- IV. If question 7 is answered 'no' or 'not relevant' but then either 'a lot' or 'a little' is ticked this is then scored 2 or 1.
- V. If two or more response options are ticked for one question, the response option with the highest score (i.e., worst) should be recorded.
- VI. The DLQI can be analyzed by calculating the score for each of its six sub-scales. When using sub-scales, if the answer to one question in a sub-scale is missing, that sub-scale should not be scored:

Symptoms and feelings	Questions 1 and 2	Score maximum 6
Daily activities	Questions 3 and 4	Score maximum 6
Leisure	Questions 5 and 6	Score maximum 6
Work and School	Question 7	Score maximum 3
Personal relationships	Questions 8 and 9	Score maximum 6
Treatment	Question 10	Score maximum 3

12.6 Analysis Visit Window

Analysis Visit	Target Day	Group 1	Group 2	Group 3*	Group 4	Group 5	Group 6
Baseline	1	Up to day 1	-	Up to day 1			
Week 1	8	2-11	2-11	-	-	-	-
Week 2	15	12-22	12-22	2-22	2-22	-	2-22
Week 4	29	23-36	23-36	23-57	23-43	2-43	23-43
Week 6	43	37-50	37-50	-	-	-	-
Week 8	57	51-64	51-64	-	44-64	44-64	44-64
Week 12	85	65-92	65-92	58-127	65-92	65-92	65-92
Week 16	113	93-120	93-120	-	93-120	93-120	93-120
Week 20	141	121-148	121-148	-	121-148	121-148	121-148
Week 24	169	149-172	149-172	128-172	149-172	149-172	149-172

Group 1: Vital signs, Physical examination, Adverse events, Prior and concomitant therapies, Hematology, blood chemistry, EASI, IGA, SCORA, Itch and sleep quality NRS, PGIS, PK sampling, Receptor occupancy and TARC.

Group 2: PGIC

Group 3: Urinalysis

Group 4: Pregnancy test

Group 5: DLQI.

Group 6: ADA sampling

*Use group 3 for ECG and TB assessment by removing week 2 and week 4 and changing the Week 12 window from '58-127' to "2-127".

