To characterize the pharmacokinetic (PK) profile of multiple doses of IMG-007 in AD participants	
 Mean serum concentration of IMG-007 over time
To evaluate the PD effect of IMG-007 on biomarkers in AD participants	
 Changes in RO and inflammatory markers including TARC in peripheral blood over time Changes in histopathology, transcriptomics and tissue biomarkers from baseline over time
To evaluate the immunogenicity of IMG-007 in AD participants	
 Occurrence of ADA after administration of IMG-007 over time

Abbreviations: AD = atopic dermatitis; ADA= anti-drug antibody; AE = adverse event; BSA = body surface area; CL = central compartment clearance; DLQI = dermatology life quality index; EASI = eczema area and severity index; EASI-50 = \geq 50% reduction from baseline in EASI; EASI-75 = \geq 75% reduction from baseline in EASI; EASI-90 = \geq 90% reduction from baseline in EASI; ECG = electrocardiogram; IGA = investigator’s global assessment;

NRS = numerical rating scale; PD = pharmacodynamic; PGIC = patient global impression of change; PGIS = patient global impression of severity; PK = pharmacokinetic; RO = receptor occupancy; SCORAD = scoring atopic dermatitis; SQ-NRS = sleep quality numerical rating scale; TARC = thymus- and activation-regulated chemokine; TEAE = treatment-emergent adverse event; WI-NRS = worst intensity itch numeric rating scale; Vc = central compartment volume

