6.5 Dose Modifications and Delays

Dose modification of the study treatment is not allowed. Any inadvertent dose modifications should be discussed with the medical monitor. Dosing should occur as close as possible on the allocated visit day and within the visit windows specified in the SoA ([Table 1](#)), except that dosing may be interrupted due to reasons stated in [Section 6.10.1.2](#). If a dose is not administered on schedule due to a visit occurring beyond the visit window specified in the SoA or dose interruption for reasons stated in [Section 6.10.1.2](#), the dose may be administered if it is no later than 5 calendar days after the allocated

visit day (a 10-calendar day delay will be allowed for the last dose at Week 4) specified in the SoA. Otherwise, the dose will be considered missed, and dosing will resume with the next scheduled dose per the SoA.

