7.4 Pharmacokinetics and Immunogenicity Assessments

Blood will be collected to describe the IMG-007 PK and immunogenicity profiles as outlined in [Table 5](#).

Participants with signs of any potential immune response to IMG-007 will be closely monitored with clinical evaluations. The PK and ADA samples may be collected at unscheduled visits for further evaluation.

Details concerning handling of PK and ADA serum samples, including labeling and shipping instructions, will be provided in the Laboratory Manual. The actual time each sample was collected will be captured to the nearest minute in the eCRF and recorded in the database.

Samples will be shipped to the laboratory where samples will be analyzed for serum IMG-007 concentrations using a validated method.

Validated screening and confirmatory assays will be employed to detect ADAs at multiple timepoints throughout the study.

The immunogenicity evaluation will utilize a risk-based immunogenicity strategy ([Bai et al. 2012](#); [Rosenberg et al. 2004](#)) to characterize ADA responses to IMG-007 in support of the clinical development program.

Table 5 PK and ADA Sampling Schema

Dose No.	Day	Pre-dose /Post-dose	PK blood sampling time	ADA sampling time	Sampling Window
1	1	Pre-dose	0 (pre-dose)	0 (pre-dose)	- 2 hours
	1	Post-dose	EOI	--	+10 mins
	8	Post-dose	7 days post-dose	--	± 3 days
2	15	Pre-dose	0 (pre-dose)	0 (pre-dose)	- 2 hours
	15	Post-dose	EOI	--	+10 mins
3	29	Pre-dose	0 (pre-dose)	0 (pre-dose)	- 2 hours
	29	Post-dose	EOI	--	+10 mins
	43	Post-dose	14 days post-dose	14 days post-dose	± 3 days
57	Post-dose	28 days post-dose	28 days post-dose	± 3 days	
	85/EOT	56 days post-dose	56 days post-dose	± 3 days	
113	Post-dose	84 days post-dose	84 days post-dose	± 3 days	
141	Post-dose	112 days post-dose	112 days post-dose	± 3 days	
169/EOS	Post-dose	140 days post-dose	140 days post-dose	± 3 days	

Abbreviations: ADA = anti-drug antibody; EOI = end of Infusion; EOT = end of treatment; EOS = end of study; PK = pharmacokinetic

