4.8 Immunogenicity Variable

The variables include anti-drug antibody (ADA) status (positive or negative) as follows:

- Total participants negative in the ADA assay at all time points analyzed
- Total participants positive in the ADA assay at any time point analyzed
- Total participants with pre-existing ADA
- Total participants with treatment emergent response
- Total participants with treatment boosted response
 - *Pre-existing ADA*: Either an ADA positive response in the assay at baseline with all post first dose ADA results negative, OR a positive response at baseline with all post first dose ADA responses less than 4-fold over baseline titer levels.
 - *Treatment-boosted response*: Pre-existing ADA that is increased to a higher concentration (4-fold or higher level) after administration of therapeutic protein product.
 - *Treatment-emergent response*: ADA developed de novo (seroconversion) following administration of therapeutic protein product in a participant who lacked detectable pre-existing ADA
 - a. *Persistent response*: Treatment-emergent response detected at 2 or more sampling time points during the treatment (including follow-up period if any), where the first and last ADA-positive samples (irrespective of any negative samples in between) are separated by a period of 16 weeks or longer.
 - b. *Indeterminate response*: as a treatment-emergent response with only the last collected sample positive in the ADA assay
 - c. *Transient response*: Treatment-emergent response detected only at 1 sampling time point during the treatment or follow-up observation period, or 2 or more time points during the treatment, where the first and last ADA-positive samples are separated by a period less than 16 weeks, and the participant's last sampling timepoint is ADA-negative.

Blood sample for the immunogenicity analysis will be collected at Day 1/Baseline (pre-dose), days 15(pre-dose), 29 (pre-dose), 43, 57, 85/EOT, 113, 141, and 169/EOS.

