6.12 Analysis of Immunogenicity Data

The ADA variables will be summarized using descriptive statistics in the immunogenicity analysis set. Frequency tables of the proportion of participants developing ADA positivity in the ADA assay, pre-existing ADA, treatment-emergent, treatment-boosted, persistent, indeterminate and transient ADA responses will be presented as absolute occurrence (n) and percent of participants (%).

Listing of ADA data will be provided.

The following summaries will be performed on the immunogenicity analysis set:

- Number (%) of patients negative ADA at all the time points analyzed
- Number (%) of patients ADA positive at time points analyzed
- Number (%) of patients with pre-existing ADA, treatment-emergent ADA, and treatment boosted ADA response
- Number (%) of patients with persistent, transient and indeterminate treatment-emergent ADA response
- Descriptive statistics of PK concentration in ADA positive and ADA negative participants.

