7.3 Analysis Visit Window

[figure not shown]
For summaries that include data collected over multiple visits, where appropriate, the data will be summarized by analysis visit window. If there are multiple measurements within a scheduled visit window (refer [Appendix 12.6](#)), the closest measurement to the scheduled timepoint of the visit will be used in the analysis. If there are two observations which have the same difference in days to the planned day, but which are not measured on the same day, the later value will be selected. If there is more than one observation on the same day then;

- Latest value will be considered in all cases except for vital signs, ECG.
- Average value will be considered in cases of continuous vital signs and ECG parameters.
- The worst value will be considered for ECG interpretation.

All measurements will be presented in the listing.

[figure not shown]

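### SAP Appendix 12.6 gives ADA sampling no Week 6 window, although an ADA sample is scheduled on Day 43 (minor)

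*SAP*

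**What the plan says.** **Sampling schedule.** SAP 4.8 lists ADA samples at baseline, Day 15 and then "29 (pre-dose), 43, 57, 85/EOT, 113, 141, and 169/EOS". Protocol Table 5 (section 7.4) has the row "43 Post-dose 14 days post-dose 14 days post-dose ± 3 days", in which the second timing entry is the ADA column. The schedule of assessments in protocol Table 1 also marks ADA at Week 6.

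**Analysis windows.** In SAP Appendix 12.6 the Week 6 row begins "Week 6 43 37-50 37-50" and has dashes for Groups 3 to 6. For Group 6, Week 4 is Days 23-43 and Week 8 is Days 44-64.

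**Selection rule.** When a window holds several records, SAP 7.3 says that "the closest measurement to the scheduled timepoint of the visit will be used in the analysis". It applies windows to multi-visit summaries where suitable and keeps every record in the listings.

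**Use of the data.** The protocol's exploratory endpoint (section 3, Table 3) is "Occurrence of ADA after administration of IMG-007 over time". One of the outputs in SAP 6.12 is "Number (%) of patients ADA positive at time points analyzed".

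**The concern.** The window table and the sampling schedule disagree about whether a Week 6 ADA sample exists. A program written from Appendix 12.6 would never produce a Week 6 ADA record. It would send each Week 6 sample to a neighbouring visit, where that visit's own sample normally wins.

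An ADA summary over time would then lack the visit that lies 14 days after the third scheduled dose. PK is in Group 1 and keeps its Week 6 window, so a comparison of concentration by ADA status, if made by visit, would have no matching Week 6 ADA record. If participant-level ADA status were also built from windowed records, a participant positive only at Week 6 would count as ADA-negative.

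**Working it through.** **Inputs**
- Post-baseline ADA days (SAP 4.8): 15, 29, 43, 57, 85, 113, 141, 169, which is 8 samples.
- Group 6 post-baseline windows (Appendix 12.6): Week 2 = 2-22, Week 4 = 23-43, Week 8 = 44-64, Week 12 = 65-92, Week 16 = 93-120, Week 20 = 121-148, Week 24 = 149-172, which is 7 windows.
- Permitted days for the Week 6 sample (protocol Table 5): 43 ± 3, i.e. Days 40-46.
- Participants enrolled (protocol 4.1): 13.

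**1. Reproduce the plan's own cut.** The boundary between Week 4 and Week 8 in Group 6 is the midpoint of their target days: (29 + 57)/2 = 43. That is the right cut for a schedule without a Week 6 visit. Group 6 matches Group 4 (pregnancy test) in every post-baseline row, and the pregnancy test has no Week 6 assessment. Copying from Group 4 is a plausible cause, but the mismatch does not depend on it.

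**2. Place each permitted Week 6 day.**

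| Day | Group 6 window | Distance from that target |
|---|---|---|
| 40 | Week 4 | 40 − 29 = 11 |
| 41 | Week 4 | 12 |
| 42 | Week 4 | 13 |
| 43 | Week 4 | 14 |
| 44 | Week 8 | 57 − 44 = 13 |
| 45 | Week 8 | 12 |
| 46 | Week 8 | 11 |

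None of the 7 days maps to Week 6.

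**3. Apply the closest-measurement rule.** An on-schedule Week 4 or Week 8 sample is at most 3 days from its target; the Week 6 sample is 11 to 14 days away.
- Against Week 4 samples on Days 26-32: 7 × 4 = 28 day combinations, and the Week 6 sample is chosen in 0.
- Against Week 8 samples on Days 54-60: 7 × 3 = 21 combinations, chosen in 0.
- A Week 4 sample delayed to Day 39 is 39 − 29 = 10 days off and still beats 11.

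If the neighbour is missing, a Day 40-43 sample can stand in only for Week 4 and a Day 44-46 sample only for Week 8.

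**4. Size.** 13 × 8 = 104 scheduled post-baseline samples. Of these 13 × 1 = 13, or 12.5%, are Week 6 samples, if everyone completes the schedule.

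**5. Only if participant-level classes use windowed records.** SAP 4.8 requires at least 16 weeks (112 days) between first and last positive samples for a persistent response. From Week 6 to Week 24 the separation is 169 − 43 = 126 days. If Week 6 is lost and Week 8 becomes the first positive, it is 169 − 57 = 112 days, exactly the limit. With ±3 days at both visits, 21 of the 7 × 7 = 49 day combinations fall below 112.

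**6. After the change.** With Week 4 = 23-36, Week 6 = 37-50 and Week 8 = 51-64, all of Days 40-46 map to Week 6; 0 of 7 are misplaced.

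**The case against.** **The SAP names no by-visit ADA table.** The 6.12 item quoted above could be read as one, but the matching variable in SAP 4.8 counts participants positive at any time point, and the neighbouring 6.12 item counts those negative throughout. The other items are mainly participant-level, and the persistence definition refers to samples, not analysis visits. Windows apply only where suitable, listings keep all records, and the mock shells are not available. This stands, and it limits the harm. It does not remove the contradiction: a column of ADA windows exists, and one of its cells conflicts with the schedule.

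**Every sample does have a window.** Days 23-43 and 44-64 are contiguous, so no Week 6 sample is unassigned. This also stands: the fault is a wrong assignment.

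**The change has a side effect.** Protocol 6.5 states that "a 10-calendar day delay will be allowed for the last dose at Week 4", i.e. up to Day 29 + 10 = 39. The present 23-43 window keeps such a late pre-dose ADA sample in Week 4. Under 37-50, Days 37-39 become Week 6, where the sample is 6, 5 or 4 days from Day 43 and loses to an on-schedule Week 6 sample. This stands as a small cost, but Group 1 already treats the PK sample from that visit in the same way.

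**If Week 6 sampling were timed from a delayed dose,** a Day 39 dose would put it on Day 53, which is Week 8 under both sets of windows. The change neither causes nor cures that.

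**Conclusion.** The contradiction is real and minor. Read literally, Appendix 12.6 misassigns every on-schedule Week 6 ADA sample, at most 13 of 104. Such a sample is left out of windowed ADA summaries when the neighbouring visit's sample is on schedule, and is labelled with the wrong visit when that sample is missing. The count assumes that all 13 participants complete the schedule; the effect assumes that some ADA output is windowed.

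Two stronger readings are tempting but not supported:

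- **That ADA-positive or persistent-response counts will be wrong.** The SAP does not say whether these classes use windowed or all records, and its definitions refer to samples. The effect in step 5 is conditional.
- **That the Week 12 efficacy window is also an error.** The row "Week 12 85 65-92 65-92 58-127 65-92 65-92 65-92" gives EASI −20/+7 days around Day 85 (85 − 65 = 20; 92 − 85 = 7). The SAP states no symmetry rule, and no visit within ±3 days is misplaced. The wide early side fits the protocol 4.1 rule that a participant withdrawing before Week 12 has the Week 12/EOT visit at withdrawal. It is a design choice, and no change is asked for.

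**What to change.** In Appendix 12.6 give Group 6 the Group 1 windows for these visits: Week 4 = 23-36, Week 6 = 37-50, Week 8 = 51-64. Leave the other windows as they are. ADA and PK samples from the same visit then carry the same label.

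Add one sentence to SAP 4.8 or 6.12: participant-level ADA status (ever positive, treatment-emergent, treatment-boosted, persistent, transient, indeterminate) is derived from all ADA samples regardless of analysis window.

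The cost is three table cells, the corresponding program constants and one sentence. Check whether any Week 4 pre-dose sample was taken on Days 37-39. If so, label ADA and PK from that visit in the same way, for example by nominal visit, and record the choice.
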